1.6 Study Rationale

Data to date from clinical trials of GEN-003 administered as a 3-dose regimen have demonstrated an acceptable safety and tolerability profile, strong and durable antibody and T-cell immune responses to both vaccine-specific antigens, production of HSV-2 neutralizing antibodies, reduction in HSV-2 shedding, and clinical benefit. This study will evaluate the effect of an additional dose of GEN-003 administered at approximately 11 to 18 months after the last dose in the primary series.

2 OBJECTIVES AND ENDPOINTS

2.1 Objectives

2.1.1 *Primary Efficacy Objective*

- To evaluate the efficacy of GEN-003 versus placebo administered as a maintenance dose in reduction of genital herpes lesion rate

2.1.2 *Secondary Efficacy Objectives*

- To evaluate the efficacy of GEN-003 versus placebo administered as a maintenance dose on genital herpes recurrence through 6 months:
 - Reduction of genital herpes recurrence frequency
 - Increase of proportion of subjects who are genital herpes recurrence-free
 - Increase of time to first genital herpes recurrence
 - Reduction of genital herpes recurrence duration

2.1.3 *Safety Objective*

- To evaluate the safety and tolerability of a maintenance dose of GEN-003 versus placebo

2.2 Endpoints

2.2.1 *Primary Efficacy Endpoint*

- Genital herpes lesion rate (proportion of days with lesions present) in the 6-month period after the maintenance dose: Based on subject report of genital lesions via a daily electronic reporting tool

2.2.2 *Secondary Efficacy Endpoints*

- Frequency of genital herpes recurrences in the 6-month period after the maintenance dose: Based on subject report of genital lesions via a daily electronic reporting tool
- Proportion of subjects genital herpes recurrence-free at 6 months after the maintenance dose: Based on subject report of genital lesions via a daily electronic reporting tool
- Time to first genital herpes recurrence in the 6-month period after the maintenance dose: Based on subject report of genital lesions via a daily electronic reporting tool
- Duration of genital herpes recurrences in the 6-month period after the maintenance dose: Based on subject report of genital lesions via a daily electronic reporting tool

2.2.3 Safety Endpoints

- Reactogenicity
 - Local reactions: Pain, tenderness, swelling, redness
 - Systemic events: Fever, headache, chills, fatigue, nausea, vomiting, diarrhea, muscle aches
- AE, SAEs, AESIs, Medically attended AEs (MAAEs)

3 STUDY DESIGN

3.1 Overall Study Design

This study is a randomized, double-blind, placebo-controlled clinical trial of GEN- 003 in subjects who have received previous doses of GEN-003. Subjects who completed Study GEN-003-003 and received all 3 doses of GEN- 003, reported data in daily electronic reporting period on at least 80% of days, and had no important protocol deviation in that trial will be offered enrollment in this study. Subjects who meet all inclusion and no exclusion criteria and provide written informed consent for this study will be randomized within 11 to 18 months after the last active GEN-003 dose in a 1:1 ratio to receive 1 IM dose (the maintenance dose) of GEN-003 or placebo. Randomization will be stratified on the basis of the GEN-003 dose received by the subject in Study GEN-003-003.

Subjects will use a daily electronic tool for reporting the presence or absence of genital herpes lesions and the severity of genital herpes symptoms from Day 1 until the Month 6 Visit.

Subjects will complete the EuroQol – 5 Domains – 5 Levels (EQ-5D-5L) questionnaire on each day of the first recurrence after the maintenance dose through Month 6.

A serum sample will be collected from each subject for future research purposes before the maintenance dose (Day 1), 7 and 28 days after the maintenance dose (Day 8 and Day 29/Month 1).

At selected investigational sites, a whole blood sample will be collected and processed to isolate peripheral blood mononuclear cells (PBMCs) for future research purposes before the maintenance dose (Day 1), 7 and 28 days after the maintenance dose (Day 8 and Day 29/Month 1).

Local reactions and systemic events will be recorded for the first 7 days after the maintenance dose on the paper Diary Card; if any event is ongoing after Day 8, it will be followed until resolution. All AEs and concomitant medications will be recorded from Day 1 to Day 29/Month 1. After Day 29/Month 1 to the end of the study, only SAEs, AESIs, MAAEs, antiviral medications, and vaccines will be recorded. All AEs will be graded in accordance with the Toxicity Grading Scale for Healthy Adult and Adolescent Volunteers Enrolled in Preventive Vaccine Clinical Trials from Grade 1 (mild) to Grade 4 (life-threatening) ([Appendix 2](#)).

From Month 2 to Month 12, the investigational site will contact each subject by telephone or site visit for review of daily electronic reporting tool data and assessment of SAEs, AESIs, and antiviral use (through Month 6).

A Data Monitoring Committee (DMC) will review safety data at intervals of a minimum of 3 months until all subjects have completed the GEN-003/placebo dosing period. Any additional meetings and the specific safety monitoring plan will be detailed in the DMC charter.

3.2 Rationale for Study Design

3.2.1 GEN-003 Dose

The selection of the 60 µg GEN-003 antigens/50 µg MM2 dose was based on a benefit/risk analysis of data from prior GEN-003 clinical trials in which various GEN-003 antigen and adjuvant doses were evaluated. In all GEN-003 clinical trials, the primary biomarker for assessing vaccine effect was anogenital HSV-2 shedding.

In Study GEN-003-001, the 30 µg antigens dose with MM2 yielded the greatest reduction in HSV-2 shedding. No safety concerns arose during this study, and increasing antigen dose did not correlate with an increased incidence or severity of AEs.

In Study GEN-003-002, the 60 µg GEN-003 antigens groups generally outperformed the 30 µg antigen dose groups, regardless of adjuvant dose, in reducing the rate of HSV-2 shedding. Within the 60 µg antigens dose groups, 50 and 75 µg doses of MM2 yielded the greater and more durable reductions in HSV-2 shedding rates than 25 µg MM2. GEN-003 exhibited an acceptable safety and reactogenicity profile in all dose combinations. The rate of Grade 3 solicited symptoms (local reactions and systemic events) appeared to be related to dose and was highest in the 60 µg GEN-003 antigens/75 µg MM2 dose; however, discontinuations due to AEs were rare and did not appear to be related to dose.

In Study GEN-003-003, the 60 µg GEN-003 antigens/50 µg MM2 dose demonstrated a greater reduction in HSV-2 shedding rate than the 60 µg GEN-003 antigens/75 µg MM2 dose. Also, 6-month data demonstrated that both active groups had similar clinical efficacy against recurrent genital herpes. The vaccine containing the higher MM2 dose was associated with a modestly higher frequency of Grade 3 solicited symptoms than the 60 µg GEN-003 antigens/50 µg MM2 dose.

In an open session of a DMC meeting during the conduct of Study GEN-003-003, Genocea requested an opinion as to whether a dose group containing the lower dose of adjuvant (25 µg) should be added. In their written response, they stated: “DSMB is not convinced of a dose response effect on AEs, therefore an additional arm at a lower dose (as proposed by the Sponsor) may not reduce AEs.”

On the basis of these results, the 60 µg GEN-003 antigens/50 µg MM2 was selected as the final dose for this and other future GEN-003 studies. This decision was supported by review of the shedding analyses and the modified intent-to-treat efficacy analyses of lesion rate, frequency, and duration of recurrence, which combined with the superior immunology and shedding responses of the 60 µg GEN-003 antigens/50 µg MM2 dose, supported the dose selection decision. Modified intent-to-treat analyses were used for the efficacy data to best represent real-world usage. The per-protocol analyses produced similar results.

3.2.2 Efficacy Endpoints

Genital herpes lesion rate in the 6-month period after the maintenance dose was selected as the primary endpoint because lesion rate is the most comprehensive measure of genital herpes disease burden. It is defined as the proportion of days with genital herpes lesions present.

Therefore, unlike other measures of vaccine efficacy, lesion rate accounts for both the frequency and duration of genital herpes disease. Use of this measure has been facilitated by technological advances in data collection methodology, namely, the development of electronic patient-reported outcomes tools that facilitate real-time daily data collection and encourages compliance through automatic reminders. In addition, assessment of lesion rate mitigates the impact of potential inconsistencies in the dataset. Endpoints related to recurrence frequency may be affected by patterns of lesion reporting that do not accurately reflect disease activity. For example, a subject may report on consecutive days: lesion – no lesion – lesion. This biologically improbable pattern may be counted as 2 recurrences, thereby increasing the estimate of disease frequency in a way that overstates true disease burden. However, this pattern of reporting would have minimal impact on lesion rate because 1 additional lesion day over the year-long follow-up period is unlikely to substantially affect the overall lesion rate.

The secondary efficacy endpoints evaluate other clinically important measures of vaccine effect, such as the frequency and duration of genital herpes recurrences.

3.3 Study Duration

The total duration of enrollment is estimated to be 2 months; the actual duration of enrollment may be longer. The duration of each subject's participation is up to 12 months. Thus, the study is expected to last approximately 14 months.

4 SUBJECT POPULATION

4.1 Inclusion Criteria

1. Completed Study GEN-003-003 (completed all study visits including the Month 12 visit)
2. Received all 3 GEN-003 doses (any dose combination) in Study GEN-003-003
3. Received last dose of GEN-003 within 11 to 18 months before the maintenance dose
4. Reported data in the daily electronic reporting period on at least 80% of days in Study GEN-003-003
5. Collected at least 45 swabs (of 56 total expected swabs) during the Month 11 to 12 swab collection period in Study GEN-003-003
6. Willing and able to provide written informed consent
7. Willing to perform and comply with all study procedures, including attending clinic visits as scheduled and completion of a daily electronic reporting tool
8. Postmenopausal (≥ 12 months with no menses without an alternative medical cause) or willing to practice a highly effective method of contraception that may include, but is not limited to, abstinence, sex only with persons of the same sex, monogamous relationship with a postmenopausal partner, monogamous relationship with vasectomized partner, vasectomy, hysterectomy, bilateral tubal ligation, licensed hormonal methods, intrauterine device (IUD), or use of a spermicide combined with a barrier method (e.g., condom, diaphragm) for 28 days before and 90 days after receiving the IP

4.2 Exclusion Criteria

1. Did not meet all eligibility criteria in Study GEN-003-003, or received incorrect treatment (treatment different from that to which they were randomized) in Study GEN-003-003
2. Use of suppressive antiviral medication within 14 days before the maintenance dose
3. Use of topical steroids or antiviral medication in the anogenital region from 14 days before the maintenance dose
4. Use of tenofovir, lysine, or other medication or supplement known or purported to affect HSV recurrence frequency or intensity from 14 days before the maintenance dose
5. History of any form of ocular HSV infection, HSV-related erythema multiforme, or herpes meningitis or encephalitis
6. Immunocompromised individuals, including those receiving any type of systemic immunosuppressive medication within 30 days prior to the maintenance dose

7. Diagnosis or suspicion of an AESI (refer to [Appendix 4](#) for list).
8. Diagnosis or suspicion of any other autoimmune disease not listed in [Appendix 4](#)
9. Vaccine-related SAE in GEN-003-003
10. Known current infection with HIV or hepatitis B or C virus
11. History of hypersensitivity to any component of the vaccine
12. Prior receipt of another vaccine containing HSV-2 antigens other than GEN-003
13. Receipt of any IP within 30 days prior to the maintenance dose of GEN-003/placebo
14. Receipt of any blood product within 90 days prior to the maintenance dose
15. Receipt of a live vaccine within 28 days prior to or any other vaccine within 14 days prior to maintenance dose
16. Planned use of any vaccine from the maintenance dose to 28 days after the maintenance dose
17. Pregnant or nursing women
18. History of drug or alcohol abuse that, in the opinion of the Investigator, would interfere with the subject's ability to comply with the requirements of the study
19. Other active, uncontrolled comorbidities that, in the opinion of the Investigator, would make the subject unsuitable for the study or unable to comply with the study requirements
20. Changes to medication used to manage an underlying comorbidity within 60 days prior to the maintenance dose

4.3 Criteria for Temporary Delay of Dosing

1. Febrile illness (temperature $\geq 38.0^{\circ}\text{C}$) or other acute illness within the past 48 hours

5 INVESTIGATIONAL PRODUCTS

5.1 GEN-003/Placebo

5.1.1 Formulation

GEN-003 consists of 2 recombinant antigens corresponding to 2 distinct HSV-2 proteins (GB208 and GB217) in combination with MM2 and diluent. Placebo is normal saline (diluent). These components are detailed in [Table 2](#).

Table 2: Composition of GEN-003

Ingredient	Description	Dose
GB208	Corresponds to a ~39 kDa internal fragment of the ICP4 protein	60 µg
GB217	A recombinant version of the glycoprotein gD modified by a deletion of the transmembrane region	60 µg
Matrix-M2 Adjuvant	An immune stimulating complex-based adjuvant containing saponin fractions purified from Quillaja saponaria (soapbark tree) bark, phosphatidylcholine, and cholesterol	50 µg
Diluent	0.9% normal saline	Not applicable

5.1.2 Packaging and Labeling

GEN-003/placebo is prepared from the following 3 components before injection:

- GB208 and GB217 antigens in a lyophilized form are supplied in a 3 mL glass vial containing 125 µg, at a concentration of 0.25 mg/mL when reconstituted to a volume of 0.5 mL.
- MM2 is supplied in a second 3 mL glass vial containing 0.75 mL of MM2 at a concentration of 1 mg/mL.
- Normal saline (0.9% sodium chloride in water) from commercially available supply is supplied in a third vial for dilution of MM2 and reconstitution of antigens to the desired concentration and for use as placebo.

The vaccine components are packaged and labeled as IPs in accordance with applicable legal and regulatory requirements.

5.1.3 Storage

The antigens and MM2 are stored at 2°C to 8°C. The site must report excursions above 8°C to the Sponsor for an assessment of product quality.

Normal saline is stored at room temperature.

5.1.4 Preparation and Administration

Preparation of GEN-003/placebo must be performed by a designated unblinded site pharmacist (or otherwise qualified personnel) in accordance with the Pharmacy Manual provided by the Sponsor. It is important to note that preparation requires approximately 30 minutes.

GEN-003/placebo will be administered by trained study personnel. Each injection will consist of a total volume of 0.5 mL administered IM to the deltoid muscle of either arm. Both 1.0-inch and 1.5-inch needles will be provided. For obese subjects, a 1.5-inch needle is recommended.

Administration of GEN-003/placebo will be temporarily delayed if the subject has had a febrile illness (temperature $\geq 38.0^{\circ}\text{C}$) or other acute illness within the past 48 hours.

5.2 Randomization

Eligible subjects will be randomized in a 1:1 ratio to receive 1 IM dose of GEN-003 (60 μg each antigen and 50 μg MM2) or placebo.

Randomization will be stratified on the basis of the GEN-003 dose received by the subject in Study GEN-003-003.

Randomization will be achieved using the randomization component of the electronic case report form (eCRF). After subject eligibility is confirmed on this form, the system will send an e-mail to the unblinded pharmacist (or otherwise qualified personnel) with instructions for accessing the treatment assignment.

5.3 Blinding and Unblinding

Subjects, Investigators, and all study staff with direct subject contact will be blinded to treatment assignment (GEN-003 vs placebo). A designated unblinded pharmacist (or otherwise qualified personnel) at each site will prepare each dose. That individual should have no contact with the subjects and minimize contact with other site study personnel.

Unblinding of treatment assignment is discouraged. In the event of a medical emergency, for which the identity of the treatment assignment is critical to the care of a subject, the Investigator should call the Medical Monitor to discuss. In the event that unblinding is deemed necessary, an unblinded statistician will provide the treatment assignment to the Medical Monitor who will provide the information to the Investigator. A decision to discontinue a subject from further IP administration is not a rationale for unblinding the treatment assignment.

An unblinded statistician will be available to the DMC and Medical Monitor and will review interim analysis.

5.4 Investigational Product Accountability, Dispensing, and Destruction

The Investigator (or designee) will maintain an accurate record of the receipt of the GEN-003 components as shipped by the Sponsor (or designee), including the date received and lot or batch

numbers. In addition, an accurate disposition record will be kept, specifying the date and lot or batch numbers administered of each GEN-003 component or placebo to each subject.

At the completion of the study, all unused IP supplies will be returned to the Sponsor (or designee) or disposed of by the site in accordance with the Sponsor's (or designee's) written instructions.

5.5 Concomitant Medications

All concomitant medications, including over-the-counter medications and supplements, will be recorded in the eCRF from Day 1 to Day 29/Month 1. Use of antiviral medications will be recorded from Day 1 through Month 6.

5.6 Prohibited Medications

5.6.1 Antiviral Medication Use for Suppression or Recurrence of Genital Herpes

5.6.1.1 Suppressive Therapy

Subjects are forbidden from taking suppressive antiviral therapy through the Month 6 Visit.

5.6.1.2 Treatment of Recurrences

Up to 3 days of antiviral treatment is permitted for recurrences.

5.6.2 Medications and Supplements with Anti-HSV Activity

Use of acyclovir, valacyclovir, famciclovir, tenofovir (except for postexposure prophylaxis for HIV-1), lysine, or other medication or supplement known or purported to affect HSV recurrence frequency or intensity is prohibited from 14 days before the maintenance dose through the Month 6 Visit (except as noted in Section 5.6.1.2 for the acute treatment of genital herpes recurrences).

5.6.3 Immunosuppressive Medications

Systemic immunosuppressive medications are prohibited from 30 days before the maintenance dose to the end of the study.

5.6.4 Vaccines

Subjects may not receive a live vaccine within 28 days prior to the maintenance dose or any other vaccine within 14 days prior to the maintenance dose. In addition, subjects may not receive any vaccine from maintenance dose to 28 days after the maintenance dose. It is particularly important to reinforce this information if the subject will be receiving GEN-003/placebo during the influenza season.

5.7 Other Study Restrictions

5.7.1 Fluid and Food Intake

There are no restrictions on fluid or food intake during the study. However, because of the large volume of blood drawn on days when PBMCs are obtained, subjects should be well-hydrated.

5.7.2 Birth Control and Prevention of HSV-2 Transmission

Male and female subjects who are not postmenopausal (≥ 12 months with no menses without an alternative medical cause) must be willing to practice a highly effective method of contraception that may include, but is not limited to, abstinence, sex only with persons of the same sex, monogamous relationship with a postmenopausal partner, monogamous relationship with vasectomized partner, vasectomy, hysterectomy, bilateral tubal ligation, licensed hormonal methods, IUD, or use of spermicide combined with barrier method (e.g., condom, diaphragm) for 28 days before the maintenance dose through 90 days after the maintenance dose.

Subjects should be advised that GEN-003 has not been proven to reduce the likelihood of transmission of HSV-2 infection to an uninfected sexual partner.

5.8 Treatment Compliance

To ensure compliance with the dosing regimen, the dose of GEN-003/placebo will be administered by trained study personnel in the clinic who have been delegated that responsibility by the Investigator.

6 STUDY PROCEDURES

Refer to [Appendix 1](#) for the Schedule of Events.

6.1 Definitions and Descriptions of Assessments and Procedures

Serum/urine pregnancy tests – For all women

Daily electronic reporting tool – Each day subjects will report the presence or absence of genital herpes lesions and genital herpes symptoms. In addition, if genital herpes symptoms are present, subjects will also rate the severity of the symptoms using the questions from the Genital Herpes Signs and Symptoms Diary ([Appendix 5](#)). Data must be entered daily through Month 6 Visit. Each subject will receive a daily reminder if data have not been entered for that day. The investigational site will receive a weekly e-mail notification if a subject has missed any data, and the site should make contact with the subject to promote compliance. Site staff will also review the data in the tool each week and at each visit.

Genital herpes lesions – Papules, pustules, vesicles, or ulcers, including those that have crusted. Symptoms of prodrome, redness, itchiness, or post-inflammatory hyperpigmentation of re-epithelialized ulcers do not constitute the presence of lesions.

EQ-5D-5L – The subject will complete this questionnaire on each day of the genital herpes first recurrence after the maintenance dose through Month 6. A pad of paper copies of the questionnaire will be provided to each subject after the maintenance dose is administered.

Reactogenicity – Subjects will be interviewed and examined at 1 hour after the maintenance dose and the following items will be entered in the eCRF:

- Local reactions: Pain, tenderness, swelling, redness
- Systemic events: Headache, chills, fatigue, nausea, vomiting, diarrhea, muscle aches
- Oral temperature

The subjects will also record these items on a paper Diary Card for the first 7 days after the maintenance dose, and the information will be entered in the eCRF.

Diary Card – Subjects will be provided a Diary Card to record local reactions, systemic events, and oral temperature for the 7 days after the maintenance dose. If there are any events ongoing after Day 8, these events will be followed until resolution and the stop date recorded. The Investigator (or Subinvestigator) will review Diary Cards with the subject. Any changes or comments to the subject's Diary Card must be made on the Diary Card and initialed and dated by the Investigator (or Subinvestigator). The Diary Card **AND** the Investigator's (or Subinvestigator's) assessment will serve as the source document. A sample of the Diary Card is provided in [Appendix 3](#).

An event recorded on the Diary Card should not be recorded on the AE eCRF unless it meets the criteria of an SAE.

AEs (including SAEs, AESIs, and MAAEs) – refer to [Section 7](#).

AEIS – refer to [Appendix 4](#) for list.

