7.1 Reporting Responsibilities

All AEs (including SAEs, AESIs, and MAAEs) will be recorded from the maintenance dose to Day 29/Month 1. After Day 29/Month 1 to the end of study, only SAEs, AESIs, and MAAEs will be recorded. It is the responsibility of the Investigator or Subinvestigator(s) to perform periodic assessment of AEs. Data describing AEs will be entered in the subject's medical record and eCRF, and as appropriate, an SAE/AESI report form. SAEs and AESIs will be reported to the Sponsor as described in Section 7.6.

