7.2.2 Medically Attended Adverse Events

A MAAE is an AE resulting in hospitalization, emergency room visit, or visit to or from medical personnel (other than routine health care visits). If a MAAE is "hospitalization" it should be reported as an SAE as described in Section 7.6 below.

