7.2.4 Serious Adverse Event

An AE or suspected adverse reaction is considered serious (an SAE) if, in the view of either the Investigator or Sponsor, it results in any of the following outcomes:

- Death
- Life-threatening (An AE is considered life-threatening if, in the view of either the Investigator or Sponsor, its occurrence places the patient or subject at immediate risk of death. It does not include an AE that, had it occurred in a more severe form, might have caused death.)
- Inpatient hospitalization or prolongation of existing hospitalization

- A persistent or significant incapacity or substantial disruption of the ability to conduct normal life functions
- A congenital anomaly/birth defect

Important medical events that may not result in death, be life-threatening, or require hospitalization may be considered serious when, based upon appropriate medical judgment, they may jeopardize the patient or subject and may require medical or surgical intervention to prevent one of the outcomes listed in this definition. Examples of such medical events include allergic bronchospasm requiring intensive treatment in an emergency room or at home, blood dyscrasias or convulsions that do not result in inpatient hospitalization, or the development of drug dependency or drug abuse.

If it is not certain that an event meets the above definitions of an SAE, contact the Medical Monitor to discuss.

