**Table 14.3.2.2: Frequency Table of Subjects with Medically Attended Adverse Events by SOC, Preferred Term and Treatment**

Safety Population		
	GEN-003 60 ug/ M2 50 ug N=xx	Placebo N=xx
MedDRA SOC Preferred Term		
Total Number (%) of Subjects With a Medically Attended AE	x (x.x)	x (x.x)
SOC1	x (x.x)	x (x.x)
PT1	x (x.x)	x (x.x)
PT2	x (x.x)	x (x.x)
---		
SOC2		
PT1	x (x.x)	x (x.x)
PT2	x (x.x)	x (x.x)
---		
-----		
SOCn		
PT1	x (x.x)	x (x.x)
PT2	x (x.x)	x (x.x)
---		

Note: Adverse event mapping was based on the MedDRA Version xx.x thesaurus.

Note: Subjects who have the same medically attended adverse event more than once are counted only once for the Preferred Term. Subjects who have more than one medically attended adverse event within a System Organ Class are counted only once in that System Organ Class.

Program:

Date Produced: mm/dd/yy

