**Listing 16.2.7.3: Adverse Events by Subject**

Safety Population  
 Treatment: GEN-003 60 ug / M2 50 ug

Subject Number	MedDRA SOC/ Preferred Term/ AE Verbatim	Start Date/ Day	Stop Date/ Day	Severity [1]	Outcome	Action Taken with Study Drug	AE Related To Study Drug	Serious	AESI	MAAE
xx-xxx		ddmmmyyyy / xxx	ddmmmyyyy / xxx	1	Fatal	None	Likely	Not Serious	Yes	Yes
				2	Not recovered	Dose delayed	Unlikely	Death	No	No
				3	Recovered	Drug withdrawn		Life Threatening		
				4	Recovered w/ sequelae			Hospitalization		
								Significant Disability		
								Congenital Anomaly or Birth Defect		
								Other medically important event		

Note: Adverse event coding was done using the MedDRA Version xx.x dictionary.  
 [1] Severity: Grade 1 = Mild; Grade 2 = Moderate; Grade 3 = Severe; Grade 4 = Potentially life-threatening  
 AESI = Adverse Event of Special Interest  
 MAAE = Medically Attended Adverse Event

Program:

Date Produced: mm/dd/yy

Programming Notes:

- Sort by Treatment, Subject number, start date, stop date, SOC, PT.
- If "Ongoing" is checked, then AE Stop Date should be missing. Put "Ongoing" in the Stop Date column.
- May need to use an 8-point font for this listing

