**Listing 16.2.7.7: Medically Attended Adverse Events by Subject**

Safety Population  
 Treatment: GEN-003 60 ug / M2 50 ug

Subject Number	MedDRA SOC/ Preferred Term/ AE Verbatim	Start Date/ Day	Stop Date/ Day	Severity [1]	Outcome	Action Taken with Study Drug	AE Related To Study Drug	Serious	AESI	MAAE	MAAE Type
xx-xxx		ddmmmyyyy / xxx	ddmmmyyyy / xxx	1	Fatal	None	Likely	Not Serious	Yes	Yes	ER Visit
				2	Not recovered	Dose delayed	Unlikely	Death	No		Other visit
				3	Recovered	Drug withdrawn		Life Threatening			
				4	Recovered w/ sequelae			Hospitalization			
								Significant Disability			
								Congenital Anomaly or Birth Defect			
								Other medically important event			

Note: Adverse event coding was done using the MedDRA Version xx.x dictionary.  
 [1] Severity: Grade 1 = Mild; Grade 2 = Moderate; Grade 3 = Severe; Grade 4 = Potentially life-threatening  
 AESI = Adverse Event of Special Interest  
 MAAE = Medically Attended Adverse Event

Program:

Date Produced: mm/dd/yy

Programming Notes:

- Sort by Treatment, Subject number, start date, stop date, SOC, PT.
- If "Ongoing" is checked, then AE Stop Date should be missing. Put "Ongoing" in the Stop Date column.
- List out all AEs where MAAE=Yes.
- May need to use an 8-point font for this listing

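### Protocol 6.1 keeps non-serious Diary Card events off the AE eCRF, so a non-serious medically attended reaction can be missing from the MAAE table and listing; secondarily, Table 14.3.1.7 can show Grade 4 only for fever

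*Protocol*

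**What the plan says.** Protocol 6.1 (Diary Card) sets the recording rule for solicited reactions: "An event recorded on the Diary Card should not be recorded on the AE eCRF unless it meets the criteria of an SAE". Seriousness is the only exception. The entry that follows refers the reader to Section 7 for AEs, including MAAEs, without saying which text prevails.

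Protocol 7.1 sets the general rule: "All AEs (including SAEs, AESIs, and MAAEs) will be recorded from the maintenance dose to Day 29/Month 1". It names the eCRF among the places where AE data are entered. Protocol 7.2.2 defines the category: "A MAAE is an AE resulting in hospitalization, emergency room visit, or visit to or from medical personnel", routine visits excepted. In Protocol 7.2.4 the nearest listed SAE outcome is narrower: "Inpatient hospitalization or prolongation of existing hospitalization". Protocol 9 has the sponsor notify the DMC Chair of every MAAE. Protocol 2.2.3 names both reactogenicity and MAAEs as safety endpoints.

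In the SAP, the MAAE flag is a column of the adverse event listings (Listing 16.2.7.3: "MAAE = Medically Attended Adverse Event"). Listing 16.2.7.7 is programmed as "List out all AEs where MAAE=Yes". Table 14.3.2.2 reports "Total Number (%) of Subjects With a Medically Attended AE" by system organ class and preferred term.

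Table 14.3.1.7 summarises solicited reactions by maximum severity, and its programming notes name the Diary Card as the source. It prints Grade 4 rows for the local items and ETC for the systemic items. The sample card (Protocol Appendix 3) scores items 0 to 3, with temperature in °F and size in mm. A SAP note says Grade 4 redness and swelling, meaning necrosis or exfoliative dermatitis, cannot be determined from the card and will be handled as an AE.

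**The concern.** A non-serious emergency room or office visit for a solicited reaction falls under two recording rules with opposite results. Under 6.1 it stays off the AE form; under 7.1 and 7.2.2 it is an MAAE and must be recorded. If sites follow 6.1, a named safety endpoint is undercounted, and the DMC Chair may not hear of the event through the route that Section 9 assumes. If sites differ in which rule they follow, the count also depends on site practice.

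The grading display adds a smaller problem. A zero printed at Grade 4 for a non-fever item would look like an observed absence, when the stated source could not have produced any other value.

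Any omission would probably fall more on the active arm. In GEN-003-003, Grade 3 reactions within 7 days of any dose occurred in 51.2% of the 60 µg/50 µg group and 13.6% of the placebo group (Protocol 1.5.5). That direction is an inference: it assumes that medical attendance rises with severity.

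**Working it through.** **Part 1: following one event through the plan.** Take injection-site pain on Day 3 that leads to an emergency room visit without admission.

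1. Pain is a Diary Card item, so the event is recorded on the card (Protocol 6.1, Appendix 3).
2. An emergency room visit makes it an MAAE (7.2.2).
3. No inpatient admission occurred, so that listed SAE outcome is not met (7.2.4). Assume it is not judged an important medical event either.
4. Under 6.1 it is not entered on the AE eCRF. Under 7.1 it is recorded.
5. If 6.1 is followed, no AE record exists to carry the MAAE flag. Neither the sample card nor the Diary Card listings (16.2.7.1, 16.2.7.2) have a field for medical attention, and the SAP names no other source. The event is absent from Listing 16.2.7.7 and Table 14.3.2.2.
6. It still appears in Table 14.3.1.7, because pain is on the card, at Grade 3 at most.

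The Listing 16.2.7.7 shell shows two MAAE types, an ER visit and another kind of visit. These are the non-hospital contacts that 6.1 can keep out.

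*Scale.* With the planned maximum of 90 subjects randomized 1:1, an arm has 90 / 2 = 45. Each subject whose only MAAE is omitted lowers that arm's percentage by 1 / 45 = 2.2 points. The documents give no rate of medical visits for reactions, so the number of such subjects cannot be estimated.

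**Part 2: which solicited items can reach Grade 4 in Table 14.3.1.7.**

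| Step | Count |
|---|---|
| Solicited items (Protocol 2.2.3): 4 local + 8 systemic | 12 |
| Grade 4 derivable from the card: fever, above 104 °F | 1 |
| Not derivable: 12 − 1 | 11 |
| Covered by the SAP note (redness and swelling in mm) | 2 |
| No note: 11 − 2 | 9 |

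The 9 are pain, tenderness, headache, chills, fatigue, nausea, vomiting, diarrhea and muscle aches.

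The table shell splits swelling into a scored row and a mm row, and the note opens with the mm rows only. By row, there are 13 in all; 13 − 1 = 12 cannot reach Grade 4 from the card, and 12 − 2 = 10 have no note (the 9 items plus scored swelling). Of those 10, Grade 4 rows are printed for 3 (pain, tenderness, scored swelling). For the 7 systemic items they are only implied by ETC.

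**How the parts meet.** For 7 of the 9 items, an emergency room visit alone is Grade 4: pain, tenderness, diarrhea, headache, fatigue and muscle aches under Appendix 2, and chills, which has no row of its own, under the fallback in 7.2.6. For nausea and vomiting (2; 7 + 2 = 9), Appendix 2 ties Grade 4 to hypotensive shock, which would probably be recorded as an SAE. A non-serious visit for one of the 7 could therefore be absent from the MAAE outputs and also shown below its Appendix 2 or 7.2.6 grade.

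**The case against.** Keeping solicited reactions off the AE form is a stated design choice that avoids double counting. Protocol 6.1 points to Section 7 for MAAEs, and Section 6.2.2 lists the Day 8 assessment of AEs, including MAAEs, separately from the Diary Card review. Section 7.2.4 lets an ER-treated event count as serious on medical judgement and sends doubtful cases to the Medical Monitor. All of this narrows the gap and makes correct recording plausible at many sites. It does not close the gap, because no text says that an MAAE overrides 6.1.

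On Grade 4, Protocol 6.1 also makes the Investigator's assessment a source. The Diary Card listings draw on the Body Symptoms-Reactions Log CRF and include the 1-hour assessment. The CRF is not in the documents, and Appendix 3 is only a sample card. That caution is fair, but those listings also stop at Grade 3, and Table 14.3.1.7 names the card as its source.

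Three stronger readings are tempting, and the documents do not support them:

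- That such a reaction would vanish from both displays. It would not; it remains in Table 14.3.1.7 at up to Grade 3.
- That 6.1 blocks the SAP's AE route for Grade 4 redness and swelling. Section 6.1 covers events recorded on the card, and the card has no field for necrosis or exfoliative dermatitis, so that route is open.
- That MAAEs will certainly be lost. A site following 7.1 would record them.

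**Conclusion.** The concern holds as a minor but real contradiction. Protocol 6.1 does not fit with 7.1, 7.2.2 and 9, and because the SAP's MAAE outputs depend on AE records, following 6.1 as written omits non-serious medically attended solicited reactions from Table 14.3.2.2 and Listing 16.2.7.7. Serious and hospitalized reactions are still captured as SAEs.

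The Grade 4 point is secondary and concerns Table 14.3.1.7 only: fever alone can reach Grade 4 from the stated source, and 9 items plus the scored swelling row have no note saying so.

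The size of any undercount is unknown and probably small. It is confined to one 7-day card after one dose, no formal testing of AEs is planned (Protocol 10.9.2), and no Grade 4 reactions were reported in GEN-003-002 or GEN-003-003 (Protocol 1.5.2, 1.5.5). The conclusion assumes that the working card and CRF match the sample card and listing shells.

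**What to change.** **Recording.** Reconcile Protocol 6.1 with 7.1, 7.2.2 and 9 by stating that a Diary Card event that is an SAE or an MAAE is also entered on the AE eCRF, with a solicited flag. Count such MAAEs in Table 14.3.2.2. The flag prevents double counting against the reactogenicity table.

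**Display.** In Table 14.3.1.7, take non-fever Grade 4 from those linked records, or mark the cells as not assessable from the Diary Card, including the scored swelling row. Footnote that, from the card, the combined rows (any systemic event; any local reaction or systemic event) can reach Grade 4 only through fever, and that the any-local-reaction row cannot reach it.

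**Cost.** One sentence in the protocol and eCRF guidelines, one flag and one footnote. If the 7-day data were already collected without linked AE records, the grading part needs only relabelled cells and the footnote. Table 14.3.2.2 would then need a note that solicited reactions recorded only on the card are not included.
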